
2.1 OBJECTIVES AND SCIENTIFIC AIMS

Primary Endpoints:

- Determine the effectiveness of the each arm by measuring Overall Response Rate [ORR = Complete Response (CR) + Partial Response (PR)] by RECIST v 1.1
- Determine Progression Free Survival (PFS) rate in each arm at 24 weeks (+/- 1 week)

- **Secondary Endpoints**

- Overall response rate in each arm evaluated by Immune-related Response Criteria in Solid Tumors (irRECIST) criteria. irRECIST assessments will only be completed for patients continuing treatment beyond PD
- Clinical benefit (CR + PR + Stable Disease [SD]) rate in each arm by 24 weeks +/- 7 days Duration of response in each arm
- Determine the rate of immune-related Adverse Events (irAE)
- Determine the rate of serious adverse events (SAE)
- Establish safety of each arm

Exploratory Endpoints:

- Determine the ability of the laboratory parameters to predict clinical benefit:
 - Archival tumor tissue PD-L1 expression IHC
 - Archival tumor tissue immune-related gene expression profiles
 - Archival tumor tissue IHC
 - Peripheral blood immune phenotyping
 - Peripheral blood gene expression profiling
 - Peripheral blood T cell receptor repertoire

Date:

- Peripheral blood serologic responses

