Target Lesions	Non-Target Lesions	New Lesions	Overall Response	Best Overall Response when Confirmation is Required*
CR	CR	No	CR	≥4 wks. Confirmation**
CR	Non-CR/Non-PD	No	PR	≥4 wks. Confirmation**
CR	Not evaluated	No	PR	
PR	Non-CR/Non-PD/not evaluated	No	PR	
SD	Non-CR/Non-PD/not evaluated	No	SD	Documented at least once ≥4 wks. from baseline**
PD	Any	Yes or No	PD	no prior SD, PR or CR
Any	PD	Yes or No	PD	
Any	Any	Yes	PD	
* See RECIST 1.1 manuscript for further details on what is evidence of a new lesion. ** Only for non-randomized trials with response as primary endpoint. *** In exceptional circumstances, unequivocal progression in non-target lesions may be accepted as disease progression. **** . Note: Patients with a global deterioration of health status requiring discontinuation of treatment without objective evidence of disease progression at that time should be reported as “ symptomatic deterioration. ” Every effort should be made to document the objective progression even after discontinuation of treatment.				
*				

For Patients with Non-Measurable Disease (i.e., Non-Target Disease)

Date:

Non-Target Lesions	New Lesions	Overall Response
CR	No	CR
Non-CR/non-PD	No	Non-CR/non-PD*
Not all evaluated	No	not evaluated
Unequivocal PD	Yes or No	PD
Any	Yes	PD
* 'Non-CR/non-PD' is preferred over 'stable disease' for non-target disease since SD is increasingly used as an endpoint for assessment of efficacy in some trials so to assign this category when no lesions can be measured is not advised		

Duration of Response

Duration of overall response: The duration of overall response is measured from the time measurement criteria are met for CR or PR (whichever is first recorded) until the first date that recurrent or progressive disease is objectively documented (taking as reference for progressive disease the smallest measurements recorded since the treatment started). The duration of overall CR is measured from the time measurement criteria are first met for CR until the first date that progressive disease is objectively documented.

Duration of stable disease: Stable disease is measured from the start of the treatment until the criteria for progression are met, taking as reference the smallest measurements recorded since the treatment started, including the baseline measurements.

Progression-Free Survival

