Progression-Free Survival (PFS) is defined as the duration of time from start of treatment to time of recurrence, progression, or death, whichever occurs first.

Survival

Survival is defined as the duration of time from start of treatment to time of death or the date of last contact whichever occurs first.

Permitted Deviations from RECIST

The study's efficacy objectives will be evaluated according to the standard, unmodified RECIST v1.1 criteria described in section 12.3, and that, within the context of this protocol, the only purpose of the modifications to the criteria is to allow certain patients to continue the study treatment despite meeting RECIST criteria for progression of disease.

The response to immunotherapy may differ from the typical responses observed with cytotoxic chemotherapy including the following ([name] et al 2009, Nishino et al 2013):

- Response to immunotherapy may be delayed
- Response to immunotherapy may occur after POD by conventional criteria
- The appearance of new lesions may not represent POD with immunotherapy
- SD while on immunotherapy may be durable and represent clinical benefit.

Date:

As long as they are receiving treatment on protocol, patients will be permitted to continue study treatment after RECIST v 1.1 criteria for POD are met if they meet all of the following criteria:

- Absence of symptoms and signs indicating unequivocal progression of disease
- No decline in ECOG performance status
- Absence of tumor growth at critical anatomical sites (e.g., leptomeningeal disease) that cannot be managed by protocol-allowed medical interventions
- Patients for whom approved therapies exist must provide verbal consent to acknowledge deferring these treatment options in favor of continuing study treatment at the time of initial apparent progression

Patients with radiographic disease progression at the at subsequent tumor assessment may be considered for continued study treatment at the discretion of the investigator if they continue to meet the criteria above and have evidence of clinical benefit.

Modification of RECIST as described may discourage the early discontinuation of durvalumab and tremelimumab and provide a more complete evaluation of its anti-tumor activity than would be seen with conventional response criteria. Nonetheless, the efficacy analysis will be conducted by programmatically deriving each efficacy endpoint based on RECIST v 1.1 criteria.

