- Progression free survival (PFS), defined as the duration of time from start of treatment to time of recurrence, progression, or death due to any cause, whichever occurs first. Patients will be censored at last follow up date. The Kaplan Meier estimate of median PFS will be reported as well as the PFS rate at 24 weeks (+/- 1 week).
- Duration of response (DOR), defined as the time from which measurement criteria are met for CR or PR (whichever status is recorded first using RECIST) until the first date of documented

Date:

disease progression, will be estimated using the Kaplan Meier method. Patients without documented progression will be censored at last follow up.

- The rate of response using immune response criteria (refer to irRECIST description in section 12.3, which defines responders and non responders) and the 90% confidence interval will be estimated using exact binomial proportions.
- Adverse events by the current version of Common Terminology Criteria for Adverse Events version 4 (CTCAE v4.03) will be tabulated in order to assess the safety profile and tolerability therapy in treated patients.

Safety Analysis

The frequency and severity of observed adverse effects will be evaluated. The rates of irAE, SAE, therapy completion rate, and protocol completion will also be reported.

Safety will be measured by the frequency of grade 3 or 4 treatment-related clinically significant toxicities (NCI Common Terminology Criteria for Adverse Events version 3.0), aside from Grade 3 or 4 hematologic or laboratory abnormalities, unless they are deemed unexpected or clinically significant.

Frequencies of toxicities will be tabulated. The grade 3 or 4 treatment-related non-hematologic/non-laboratory toxicity will be estimated at the end of the trial along with the 95% confidence interval. With 40 patients per arm, these rates can be estimated within $\pm 16\%$.

Methods of Efficacy Analysis

Efficacy Variables

The intent of this protocol is to assess checkpoint inhibitors for activity in patients with carcinomas advanced, recurrent endometrial carcinomas and carcinosarcomas.

The principal parameters employed to evaluate the efficacy of the two arms are:

- The rate of ORR and duration of overall objective response (ORR = CR + PR).
- Progression-free survival rate at 24 weeks for all patients evaluable for this endpoint.
- Clinical Benefit Rate (CBR) will be defined as ORR + Stable Disease (SD) rate by 24 weeks.

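### Duration of response censors responders who die without documented progression, although the same death is a PFS event

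*Combined protocol and SAP*

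**What the plan says.** Section 14.0, Definitions of Statistics to be Reported, starts DOR when CR or PR is first recorded and stops it at documented progression. It then adds: "Patients without documented progression will be censored at last follow up". Section 12.4, Duration of Response, gives the same end point with recurrence added: DOR runs "until the first date that recurrent or progressive disease is objectively documented". Neither place names death.

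In the same Section 14.0 list, PFS runs to "time of recurrence, progression, or death due to any cause, whichever occurs first", with the censoring rule "Patients will be censored at last follow up date". The Efficacy Variables part of Section 14.0 repeats last follow-up as the censoring date for an evaluable patient followed for less than six months. No section defines that date. For survival, Section 12.4 uses a different term: "to time of death or the date of last contact whichever occurs first".

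DOR is a secondary endpoint in Section 2.1 ("Duration of response in each arm"). Section 14.0 also places it among the principal efficacy parameters ("The rate of ORR and duration of overall objective response"). It has no test and no threshold.

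**The concern.** A death on study ends a response as surely as progression does. If it is censored, Kaplan-Meier treats the patient as someone whose response could have continued and who was merely lost from view. The reported figure is then time to progression with deaths removed, and readers may take it for how long patients lived with a response.

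Two routes lead there. One is death from an adverse event during response. The other is the category in Section 12.4 for "global deterioration of health status requiring discontinuation of treatment without objective evidence of disease progression". That section asks for every effort to document progression later, but a patient may die first.

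What is at stake is the DOR estimate in each arm, which will be read beside ORR as evidence of activity.

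**Working it through.** **The plan's own figures.** The plan gives no number for DOR. Its nearest stated figures reproduce by exact binomial calculation:
- The PFS rule (at least 10 of 40; 15% against 35%) has Type I error 6.7% and power 93.6%, against the stated 7% and 94%.
- The ORR rule (at least 3 of 27, then at least 7 of 40; 10% against 25%) has 9.8% and 90.0%, against the stated 10% and 90%.

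Neither calculation uses DOR, so neither changes.

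**Direction.** Take a death as the end of that patient's follow-up. Counting it as an event multiplies the Kaplan-Meier curve at that time by a factor below 1; censoring it multiplies by 1. The risk sets at all other times are the same. The curve with deaths censored is therefore never below the curve with deaths counted. This strict ordering needs the censoring date to be the date of death. With an earlier date, other responders' events in the gap would meet a smaller risk set, and a single data set could depart from it.

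**Size.** Let M be the true median DOR with deaths counted, and s the share of response-ending events that are deaths without documented progression. With constant hazards:
- total hazard = ln 2 / M
- progression hazard = (1 - s) × ln 2 / M
- median with deaths censored = M / (1 - s)

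The documents give neither s nor M, so both are assumed here:

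| s | inflation 1/(1 - s) | M = 12 months reads |
|---|---|---|
| 5% | 1/0.95 = 1.053 | 12.6 months |
| 10% | 1/0.90 = 1.111 | 13.3 months |

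Section 3.0 shows only that such deaths can occur. On durvalumab, 15 of 303 patients (5.0%) died of an adverse event, 2 of them coded as disease progression. On the combination, 2 of 102 (2.0%) had treatment-related Grade 5 events. These are shares of all treated lung cancer patients, not of responders' first events, so they do not estimate s.

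**One reclassified death.** Suppose 7 responders, the ORR threshold, end at 2, 4, 6, 8, 10, 12 and 14 months.
- All counted: the curve is 4/7 = 0.571 after month 6 and 3/7 = 0.429 after month 8. The median is 8 months.
- Month-4 event censored: 6/7 = 0.857; then × 4/5 = 0.686 at month 6, × 3/4 = 0.514 at month 8, × 2/3 = 0.343 at month 10. The median is 10 months.

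**Against sampling noise.** In 20,000 simulated arms of 7 responders (constant hazards, no other censoring), censoring the deaths lengthened the median in 14% of arms at s = 5% and in 28% at s = 10%, and never shortened it. With deaths counted and a true median set at 7.2 months for scale, 90% of observed medians fell between 2.6 and 15.6 months. That is 2.6/7.2 = 0.36 to 15.6/7.2 = 2.17 times the truth. A shift of 1.05 or 1.11 is small beside that range.

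**The case against.** The strongest reply is that both sections give essentially the same definition of DOR: time to progression among responders. That is a coherent, stated quantity with no test attached, and the rule for choosing between arms names ORR, PFS and safety but not DOR. This stands as far as it goes: there is no contradiction and no decision is exposed. It does not remove the one-directional effect on a reported efficacy figure, which a confidence interval will not show.

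A reader might infer a large effect: the same formula gives +25% or +43% if s were 20% or 30%. Nothing in the documents supports shares of that size.

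A reader might also infer that the undefined last follow-up inflates the Kaplan-Meier 24-week PFS rate, because a phone contact could count as progression-free time. Section 4.3 does word scans after stopping treatment without progression as optional, and Appendix A provides phone contact for survival status. But that row covers only patients who refuse to return. Appendix A, to which Section 9.1 refers, also schedules scans until progression for patients who stop durvalumab for toxicity or symptomatic deterioration. Section 17.2.1.1 likewise assumes that tumour assessments go on after stopping for reasons other than progression. No document gives a share of patients who stop being scanned, and if the term means the last scan there is no such credit. The documents therefore support a request for a definition, not a claim of bias.

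**Conclusion.** The DOR point holds as an explicit rule, not as missing detail. Responders who die without documented progression are censored, and this lengthens the Kaplan-Meier DOR or leaves it unchanged. The inflation of the median is 1/(1 - s) under constant hazards: about 5% or 11% at an assumed s of 5% or 10%. That is within sampling noise at about 7 responders per arm. The result rests on constant hazards, on follow-up ending at the death, and on values of s that the documents do not supply.

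The ORR rule, the 10% error bound, the 10-of-40 PFS rule and the sample size are unaffected. The censoring date for PFS and DOR needs defining, but no bias from it has been shown. The change should be made because it is cheap and removes a one-sided effect; it does not threaten the trial's conclusions.

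**What to change.** **Main change.** In Sections 12.4 and 14.0, define DOR as the time from first CR or PR to first documented progression or death from any cause, whichever comes first, using the same wording in both places.

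**Clarifications.**
- In both places in Section 14.0 that use last follow-up, state that patients without a PFS or DOR event are censored at the last adequate tumour assessment.
- State how a death after missed scans is handled. Otherwise a patient no longer scanned stays at risk until death, and the new censoring rule does not reach that patient.
- Reconcile the optional wording on scans in Section 4.3 with Section 17.2.1.1 and Appendix A, which have them continuing until progression.
- Leave the 10-of-40 rule as it is, including its treatment of short follow-up as failure.

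**Cost.** Protocol wording and programming only. Response assessments are already captured (Section 16.1), as are dates of death for serious adverse events (Section 17.3.1) and survival status (Appendix A). The PFS definition needs the same death dates in any case. The downside is that DOR becomes time to progression or death and may look slightly shorter.

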4.1 OVERVIEW OF STUDY DESIGN/INTERVENTION

4.2 Design

This is an MSKCC investigator-initiated, single-center, randomized, open-label, phase 2 study to evaluate the activity of durvalumab alone (Arm 1) or durvalumab in combination with tremelimumab (Arm 2) in patients with recurrent or persistent endometrial carcinoma or endometrial carcinosarcoma. The safety and tolerability of these agents in this patient population will also be evaluated.

Patients will be randomized to Arm 1: durvalumab alone or Arm 2: durvalumab with tremelimumab. Randomization will be accomplished by the method of random permuted block, and patients will be stratified by histology (stratum 1: endometrial carcinosarcoma patients OR MSI-high endometrial carcinoma patients and stratum 2: other histologies). We will limit enrollment of stratum 1 to 10 patients per arm.

MSI-high patients will be identified based on immunohistochemistry or MSI testing of tumor by department of pathology or via known mutations found in mismatch repair genes via the Integrated Mutation Profilng of Actionable Cancer Targets (IMPACT) assay through MSKCC IRB# 12-245.

Each cycle will be 28 days in duration. Patients will receive study treatment until disease progression, intolerable toxicity, elective withdrawal from the study, study completion, or study termination.

Radiologic tumor assessment will be repeated every 8 weeks +/- 7 days for the first 48 weeks and then every 12 weeks +/- 7 days until PD. For patients who remain progression free 2 years post completion of protocol directed treatment, every 6 months +/- 1 month. Safety will be evaluated through the monitoring of all serious and non-serious AEs and irAE's, graded according to the current version of National Cancer Institute's Common Terminology Criteria for Adverse Events (CTCAE v. 4.03).

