Radiologic tumor assessment will be repeated every 8 weeks ± 7 days for the first 48 weeks and then every 12 weeks ± 7 days until PD. For patients who remain progression free 2 years post completion of protocol directed treatment, every 6 months ± 1 month. Patients who discontinue treatment for reasons other than progression may continue efficacy assessments until progression is demonstrated. Patients who demonstrate radiologic progression by RECIST criteria may be considered for continued therapy (but not primary efficacy analysis) if they are deemed to be clinically benefiting, according to predetermined permitted criteria (section 12.4). Safety will be evaluated in this study through the monitoring of all serious and non-serious AEs and irAEs, graded according to the current version of the National Cancer Institute Common Terminology Criteria for Adverse Events (CTC v.4.03).

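### The only toxicity rate with a confidence interval stops at grade 4, and its defining sentence cites CTCAE v3.0 in a trial graded under v4.03

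*Combined protocol and SAP*

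**What the plan says.** Section 14.0, Safety Analysis, defines the safety measure: "Safety will be measured by the frequency of grade 3 or 4 treatment-related clinically significant toxicities". The same sentence gives the grading system as "NCI Common Terminology Criteria for Adverse Events version 3.0" and sets aside hematologic and laboratory abnormalities unless they are unexpected or clinically significant.

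The next paragraph says "The grade 3 or 4 treatment-related non-hematologic/non-laboratory toxicity will be estimated at the end of the trial", with a 95% confidence interval. It adds "With 40 patients per arm, these rates can be estimated within" ±16%. The interval sentence names no CTCAE version; v3.0 comes from the definition just before it.

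The other safety rates carry no interval: "The rates of irAE, SAE, therapy completion rate, and protocol completion will also be reported".

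Elsewhere the version is 4.03:
- Section 14.0, Definitions of Statistics to be Reported: "Common Terminology Criteria for Adverse Events version 4 (CTCAE v4.03) will be tabulated".
- Section 4.2: "Common Terminology Criteria for Adverse Events (CTCAE v. 4.03").
- Section 4.3: "National Cancer Institute Common Terminology Criteria for Adverse Events (CTC v.4.03").
- Section 11.1 says that all toxicities are graded under v4.03.

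The safety set is worded in two ways. Section 14.0 (Methods of Efficacy Analysis) asks for at least one cycle of therapy. Section 12.1 (Definitions) makes every patient evaluable for toxicity from first treatment.

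If both arms reach 7 responders, Section 14.0 picks the arm with the higher ORR. If both have exactly 7, a review of efficacy and safety decides, and its safety part refers to the number and type of grade 3 events.

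**The concern.** Establishing the safety of each arm is a secondary endpoint (Section 2.1). The one toxicity rate that the plan formally estimates leaves out the most severe grade. An analyst who follows the text would score a patient with a fatal treatment-related event, and no other qualifying event, as free of severe toxicity. Any such omission can only lower the rate.

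The documents show that the situation can arise. Section 3.0 reports treatment-related grade 5 events with durvalumab alone and with the combination. A patient who dies in cycle 1 could also be left out of the denominator if one cycle is read as a completed 28-day cycle.

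The version conflict leaves the measure defined under a system that the trial does not grade with.

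**Working it through.** **1. The plan's own figure.** Inputs: n = 40 per arm and a 95% interval (Section 14.0), at the worst case p = 0.5.
- Normal approximation: 1.96 × √(0.5 × 0.5 / 40) = 0.155.
- Exact binomial at 20/40: 0.338 to 0.662, half-width 0.162.

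Both round to the stated ±16%. The figure depends on n, so counting grade 5 does not change it.

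**2. Size of one omission.** 1/40 = 2.5 percentage points. As an illustration with assumed counts, let 8 of 40 patients have a qualifying event, one of them only a fatal event in cycle 1.
- Grades 3 to 5: 8/40 = 20.0%.
- As written: 7/40 = 17.5%.
- As written, and if she is also dropped from the safety set: 7/39 = 17.9%.

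**3. How often it might happen.** Inputs from Section 3.0, Potential risks:
- Monotherapy (Study 1108): 1 of 694 had a treatment-related grade 5 event.
- Combination (Study D4190C00006): 2 of 102 did. One of these two also had a grade 4 event and would be counted anyway, so at most 1 of 102 would be missed.

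If these rates carried over, the chance of at least one missed patient among 40 is at most:
- Combination: 1 − (101/102)^40 = 0.33.
- Monotherapy: 1 − (693/694)^40 = 0.056.

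The 102 combination patients include cohorts at higher tremelimumab doses than this trial's, which Section 3.0 describes as more toxic. The 33% is therefore an illustrative upper figure.

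**4. The tie review (minor).** Assume two independent arms with 40 evaluable patients each. An arm is positive with at least 3 responders in 27 and at least 7 in 40. The probability that an arm passes stage 1 and ends with k responders is the sum, over x from 3 to 27, of Bin(x; 27, p) × Bin(k − x; 13, p). A tie at k has probability P_A(k) × P_B(k). At p = 0.25 in both arms, P(7) = 0.0834, so a tie at 7 has probability 0.0834² = 0.0070. Summing the products over k from 8 to 40 gives 0.0915.

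| True ORR, arms | Tie at 7 (rule exists) | Tie at 8 or more (no rule) |
|---|---|---|
| 25% / 25% | 0.7% | 9.2% |
| 20% / 20% | 2.2% | 6.3% |
| 25% / 35% | 0.1% | 5.9% |
| 15% / 25% | 1.2% | 3.1% |
| 10% / 25% | 0.5% | 0.5% |

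**The case against.** The strongest reply is that little is lost. Death is a criterion for an SAE (Section 11.4.2), the SAE rate is reported, and all adverse events are tabulated under v4.03. Section 17.3.1 records changes in grade as well as the maximum, so an event that passed through grade 3 or 4 can still be counted. A shift of 2.5 points is small against ±16%. All of this stands, and it limits the point to one rate.

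The version is probably a stale citation. Section 11.1 settles how events are graded, so a reader who infers that some events would be graded under v3.0 goes beyond the text. The conflict still needs correcting.

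The two safety sets may also be the same patients, because drug is given on Day 1 of each cycle. That is a fair reading. The 7/39 figure depends on the other one, which the wording permits.

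On ties, a reader might infer that unequal evaluable denominators make the winner rule contradict itself, since Section 9.1 does not replace withdrawn patients. The documents do not support much of this. Section 14.0 continues accrual to 40 patients per arm and points to the evaluability definition. If denominators did differ, equal counts of 8 or more would already be settled by the higher-ORR clause. Only the 7–7 case would meet both clauses, and the specific clause would naturally govern it.

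**Conclusion.** The point holds in a limited form. As written, the only toxicity rate with an interval scores a patient whose sole qualifying event is a treatment-related death as event-free, and its defining sentence cites the wrong grading version. The size is 2.5 percentage points per such patient with 40 patients. The chance of at least one is at most about 33% in the combination arm and 5.6% in the monotherapy arm, if the earlier rates in Section 3.0 apply here.

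A reader might infer that deaths go unreported or that the conclusion about an arm could change. Neither follows: deaths are reported elsewhere, and no decision rule uses this rate.

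The tie matter is minor. Tied arms have each met their own ORR rule, the trial is not powered to compare them, and the existing tie-break is itself a discretionary review. The missing rule for ties at 8 or more is a gap in detail. The tie probabilities rest on independent arms, 40 evaluable patients in each, and the assumed true ORRs.

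**What to change.** In Section 14.0:
- Safety Analysis: change grade 3 or 4 to grade 3 or higher (grades 3 to 5) in both the measure sentence and the interval sentence.
- Safety Analysis: change version 3.0 to v4.03.
- Methods of Efficacy Analysis: define the safety set as all patients who received any study treatment, to match Section 12.1.
- Minor: in the tie review, refer to adverse events of grade 3 or higher. The review could also apply to any tie in ORR when both arms have 7 or more responders.

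The cost is wording only. Maximum grade is already collected (Section 17.3.1). The reported rate may be slightly higher, and the ±16% stays. Neither arm's ORR or PFS decision changes, nor do the error rates or the sample size. The tie edit extends the existing review and leaves its discretion in place.
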